3.2 Potential Risks and Benefits to Human Patients

PP-001 is a novel chemical molecule, designed to inhibit an enzyme called DHODH, a known drug target for systemic treatment of rheumatoid arthritis and multiple sclerosis. PP-001 is a novel inhibitor of DHODH and has the potential to deliver a new treatment for patients with AKC. Currently, patients suffering from AKC are not treated with any drug-based therapy.

In the present study the safety and tolerability of multiple doses of PP-001, administered via eye drops as a single dose and over 12 days (48 doses), will be evaluated. Based on the pharmacokinetic results from the previous study (PP-001-1001) the ocular half-life is expected to be less than 9 h and the systemic exposure is expected to be below the biological activity and close to or below the limit of detection (10 ng/mL). Therefore, this study poses limited risk to the healthy subjects enrolled.

This study will identify the tolerated doses at expected efficacious ocular exposures and will serve as the basis for further studies of long term acting PP-001.

The inclusion and exclusion criteria prevent individuals with eye disorders, which may be adversely affected by exposure to the IP, from entering the study.

At this stage of development, toxicity of PP-001 in human eyes cannot be ruled out but the risk is considered low based on the safety factor calculated using preclinical data. Considering the expected low systemic exposure of PP-001, potential side effects seen with other DHODH inhibitors are not expected to occur.

In conclusion, based on the currently available safety data, and at doses in the estimated therapeutic range of up to 3.0 mg/mL and four daily drops/eye, PP-001 has an acceptable benefit/risk profile in this study population. Study PP-001-1101 will provide valuable data on the safety, tolerance and pharmacokinetic profile of PP-001 following a single dose and over 12 days (48 doses), via eye drops in healthy subjects, which will help to define the dose and formulation for future studies.

4. STUDY POPULATION

4.1 Inclusion Criteria

Cohorts 1-3:

All subjects must meet all of the following criteria to be included in the study:

1. Male or female healthy volunteers 18–64 years of age.

2. Good general state of health (mentally and physically). Laboratory parameters and vital signs of subjects must be within the normal ranges (or judged as not clinically significant by the investigator) and subjects must not have a diagnosis of any eye or systemic disease that could affect the pharmacokinetics of PP-001.
3. Willing to provide a signed and dated written informed consent form.
4. Female subjects of childbearing potential must have a negative urine pregnancy test prior to the first administration on Day 0.
5. Male and female subjects must ensure that one highly effective method of contraception, combined with an acceptable method of contraception, is used for the entire duration of the study, from first dose up to the study follow-up visit. Subjects must agree to refrain from becoming pregnant or fathering a child in the 3 months following the last study drug administration. Male subjects must agree with their female partners, prior to screening, to use the above specified methods of contraception while receiving IP, and for 3 months after stopping IP.
6. Best-corrected visual acuity of 0.1 log minimal angle of resolution or better in both eyes (approximately 20/25 or better).
7. Intraocular pressure <21 mmHg with differences between eyes of <4 mmHg.

Cohort 4:

All subjects must meet all of the following criteria to be included in the study:

1. Male or female subjects 18–64 years of age with ocular surface inflammation in both eyes as defined below.
2. Ocular surface inflammation defined as an Ocular Surface Disease Index (OSDI) of 22 or more AND conjunctival hyperemia of Grade 2 on the Efron Scale or more in both eyes
3. Good general state of health (mentally and physically). Laboratory parameters and vital signs of subjects must be within the normal ranges (or judged as not clinically significant by the investigator) and subjects must not have a diagnosis of any eye disease except ocular surface inflammation.
4. Willing to provide a signed and dated written informed consent form.
5. Female subjects of childbearing potential must have a negative urine pregnancy test prior to the first administration

6. Male and female subjects must ensure that one highly effective method of contraception, combined with an acceptable method of contraception, is used for the entire duration of the study, from first dose up to the study follow-up visit. Subjects must agree to refrain from becoming pregnant or fathering a child in the 3 months following the last study drug administration. Male subjects must agree with their female partners, prior to screening, to use the above specified methods of contraception while receiving IP, and for 3 months after stopping IP.
7. Best-corrected visual acuity of 0.1 log minimal angle of resolution or better in both eyes (approximately 20/25 or better).
8. Intraocular pressure <21 mmHg with differences between eyes of <4 mmHg.

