5.2 Timing of Dosing and Dose Administration

Cohorts 1-3:

Subjects will receive IP on Day 0 (single dose) and then Days 8–19 (48 doses).

On Day 0, the IP dose will be administered in house by site staff. Staff will administer a single drop of IP into one eye.

On Day 8 and 9, the IP doses will be administered in house by site staff. Staff will administer a single drop of IP into one eye four times throughout the dosing day separated by at least 4 hours.

On Days 10–19, the IP will be self-administered. Subjects will administer a single drop of IP into one eye four times throughout each dosing day separated by at least 4 hours.

Cohort 4:

Subjects will receive IP on Days 0-11 (24 doses).

On Day 0 and 1, the first instillation will be performed in house by site staff. Staff will administer a single drop of IP into one eye. At all following time points, the IP will be self-administered. Subjects will administer a single drop of IP into one eye two times throughout each dosing day separated by at least 8 hours.

Since only one randomly assigned eye will be treated, subjects will be handed out a bottle of topical lubricants (Genteal HA, Laboratoires Thea, France) as standard of care treatment for the control eye as needed. Subjects will be instructed to document instillation dates and times for Genteal HA eye drops in the diary.

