6.10 Contraceptive measures

Women of childbearing potential and fertile men need to adhere to contraceptive measures in accordance with the "Recommendations related to contraception and pregnancy testing in clinical trials, September 2014" of the Clinical Trials Facilitation Group.

Male and female subjects must ensure that one highly effective method of contraception combined with an acceptable method of contraception is used for the entire duration of the study, from first dose up to the study follow-up visit, and must refrain from becoming pregnant or fathering a child in the 3 months following the last study drug administration. Male subjects must agree with their female partners prior to screening to use the above specified methods of contraception while receiving protocol-specified medication, and for 3 months after stopping the medication.

- Highly effective methods of birth control are defined as those that result in a low failure (i.e., < 1 % per year) when used consistently and correctly, such as:
 - combined (oestrogen and progestogen containing) hormonal contraception associated with inhibition of ovulation (oral, intravaginal, transdermal)
 - progestogen-only hormonal contraception associated with inhibition of ovulation (oral, injectable, implantable)
 - intrauterine device
 - intrauterine hormone-releasing system
 - bilateral tubal occlusion

- vasectomised partner
- sexual abstinence
- Acceptable birth control methods are defined as those that result in a failure rate of more than 1% per year and include:
 - progestogen-only hormonal contraception, where inhibition of ovulation is not the primary mode of action
 - male or female condom with or without spermicide
 - cap, diaphragm or sponge with spermicide

Periodic abstinence and withdrawal are not acceptable methods of contraception. Female partners of male subjects must be informed by their male partners about the need to use one highly effective methods of birth control combined with an acceptable method of birth control as defined above.

Female subjects of childbearing potential must perform a negative urine pregnancy test prior to the first instillation of PP-001. In cohorts 1-3, an additional urine pregnancy tests will be performed during the safety visit on Study Day 8 and Study Day 28. In cohort 4, urine pregnancy tests will be performed at screening, on Study day 0 and on Study Day 20.

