7.4 Other Reportable Events

Certain events that occur in the absence of an AE should be reported to the Sponsor as Other Reportable Events. These include the following:

- Pregnancy exposure (subject becomes pregnant while taking study drug)
 - Subjects who are pregnant at Screening are not permitted to take part in this study; however, Panoptes Pharma GesmbH or their representative must be notified of any subjects that become pregnant while participating in this study (or the partner of a male subject). Although pregnancy is not technically an AE, all pregnancies must be followed to conclusion to determine their outcome. This information is important for both drug safety and public health concerns. It is the responsibility of the Investigator or designee to report any pregnancy in a subject that occurs during this study to Panoptes Pharma GesmbH or their representative.
- Lactation exposure (subject is taking study drug while nursing an infant)
- Accidental exposure (someone other than the study subject is exposed to study drug)
- Overdose (subject receives more than the prescribed dose of study drug within a given timeframe)
- Other medication errors that potentially places subjects at a greater risk of harm than is previously known or recognised (e.g., study drug is administered by an incorrect route)

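### The contraception and no-pregnancy rules end on different dates, and pregnancy reporting stops with the study, leaving about 82 of the 91 days after the last dose outside the reporting rule

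*Protocol*

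**What the plan says.** Protocol 4.1 (criterion 5 for Cohorts 1-3, criterion 6 for Cohort 4) contains three time limits in one item:

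- For men and women, a highly effective method plus an acceptable method "is used for the entire duration of the study, from first dose up to the study follow-up visit".
- For all subjects: "Subjects must agree to refrain from becoming pregnant or fathering a child in the 3 months following the last study drug administration".
- For male subjects only, an agreement with their partners "to use the above specified methods of contraception while receiving IP, and for 3 months after stopping IP".

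The synopsis repeats this text. Section 6.10 joins the first two limits in one sentence ("from first dose up to the study follow-up visit, and must refrain from becoming pregnant or fathering a child in the 3 months following"), counted from the final dose, and again gives the 3-month method rule to men only.

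Protocol 7.4 describes pregnancy reporting three times. The event is titled "Pregnancy exposure (subject becomes pregnant while taking study drug". The notification sentence covers subjects, and partners of male subjects, for as long as the subject takes part in the study. The investigator's duty is "to report any pregnancy in a subject that occurs during this study". The requirement to follow pregnancies to their outcome sits in the same item.

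Sections 7 and 7.3 end adverse event and serious adverse event collection at the follow-up visit. Tables 1 and 2 schedule nothing after it.

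**The concern.** The protocol defines a 3-month period in which pregnancy is to be avoided, but the rules meant to support that period stop earlier and at different points. A male subject finds two end dates for the same methods. A female subject finds an explicit method rule that ends at follow-up and a duty to avoid pregnancy that does not. An investigator who follows 7.4 literally has no duty to report a conception, in a subject or a partner, that occurs after the last visit but within the 3 months.

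What is at stake is safety information. Section 7.4 itself says that pregnancy outcomes matter for drug safety and public health. PP-001 inhibits an enzyme needed for pyrimidine, and hence RNA and DNA, synthesis (1.3), and the toxicology summary in 1.3 names no reproductive or developmental study. Sample size, the primary endpoint and the analyses in the SAP are not affected.

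**Working it through.** **Timeline inputs**

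- Cohort 4, last dose: Day 11 (5.2: "Subjects will receive IP on Days 0-11 (24 doses").
- Cohort 4, follow-up and last pregnancy test: Day 20 (6.10: "In cohort 4, urine pregnancy tests will be performed at screening, on Study day 0 and on Study Day 20"), with a window of ±1 day in Table 2.
- Cohorts 1-3, last dose: Day 19 (5.2). Follow-up and last pregnancy test: Day 28 (6.10), ±1 day in Table 1.

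**Reproducing the plan's own figures.** Screening runs from Day -14 to Day -2.

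- Cohort 4: 2 + 20 = 22 days minimum and 14 + 21 = 35 days maximum. Both match Section 3.
- Cohorts 1-3: 2 + 28 = 30 and 14 + 28 = 42 days. Both match, the maximum without the extra window day.
- Doses: 12 × 2 = 24 and 12 × 4 = 48. Both match.

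**Gap from last dose to follow-up**

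- Cohort 4: 20 − 11 = 9 days. Cohorts 1-3: 28 − 19 = 9 days.
- With the ±1 day window: 8 to 10 days in both.

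**Share of the 3 months after follow-up.** The documents give no day count for 3 months, so I assume 91 days and vary it. Share = (days in 3 months − gap) / days in 3 months.

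- Base case: (91 − 9) / 91 = 82/91 = 90.1%.
- Calendar readings of 89 to 92 days, gap 8 to 10: from (89 − 10)/89 = 88.8% to (92 − 8)/92 = 91.3%.
- Read as 84 days (12 weeks): from (84 − 10)/84 = 88.1% to (84 − 8)/84 = 90.5%.

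**The three scopes in 7.4 against the 91 days after the last dose**

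- While taking study drug: 0 of 91 days covered.
- While taking part in the study: 9 of 91 covered, 82 not.
- During the study: 9 of 91 covered, 82 not, if the study ends for a subject at the last follow-up, which is how Section 3 measures duration.

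**The method rule, by sex**

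- Men: one sentence ends it at follow-up, another 3 months after stopping treatment. These conflict unless the longer is meant to prevail.
- Women: the explicit two-method wording ends at follow-up. Only the duty not to become pregnant continues.

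**The case against.** The strongest reply is that the limits are nested, not contradictory: two methods until follow-up, then a duty on everyone to avoid pregnancy for the rest of the 3 months. A subject can satisfy both, and a woman who stops contraception and conceives within 3 months breaches the second sentence of the same criterion. This stands in part. A reader might infer that women have no obligation after follow-up, and the documents do not support that. The 3-month duty applies to them. Section 6.10 also requires adherence to a named external recommendation, and the exclusion criteria in 4.2 bar women who are planning a pregnancy or unwilling to use reliable contraception; neither has an end date. The external text is not available here, so what it requires after follow-up is unknown.

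A reader might also infer that the sponsor could never learn of a later pregnancy. That goes too far. The consent text is not among the pages available and may ask subjects to report one, and 7.4 does not forbid a later report. The phrase about pregnancies during the study could also be read as the trial as a whole, which would cover some subjects for longer. What remains is that 7.4, as written, does not require reporting across the 3 months.

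Finally, the 90% could be mistaken for a level of risk. The protocol expects an ocular half-life under 9 hours and systemic exposure near or below the detection limit (3.2), and reports no detectable plasma PP-001 after intravitreal injection (1.4). Nine days is 216 hours, or 24 half-lives at 9 hours. These expectations reduce the likely harm, but they do not explain a 3-month restriction without a matching reporting rule.

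**Conclusion.** The point holds as a mismatch between stated periods. The method end dates conflict for men and are left open for women after follow-up. Section 7.4 has three differing reporting scopes, and none extends past the study. About 82 of 91 days (88% to 91% across readings) of the protocol's own period fall outside the reporting rule, for subjects and for partners of male subjects.

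This rests on three assumptions: 3 months is 84 to 92 days; a subject's participation ends at the last follow-up visit; and, for Cohorts 1-3, later visits move with dosing when Part II starts after Day 8. The percentage is calendar time only and says nothing about the chance of a pregnancy or of harm. Which duration is right is not judged here.

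The change is worth making because it is cheap and specific. Its reach is limited: SAP 2.11 records that Cohorts 1-3 began recruiting in November 2018, that Cohort 3 was stopped prematurely after the June 2019 hold, and that Cohort 4 recruits from May 2021. An amendment can therefore act only on Cohort 4 (21 subjects, 14 on PP-001).

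**What to change.** - Reconcile the end dates in the synopsis, 4.1 and 6.10, so that the method rule and the no-pregnancy rule can be read together without conflict for each sex. The sponsor settles the duration.
- In 7.4, replace all three limiting phrases with a single reporting period. It should keep the in-study coverage that exists now, end when the confirmed no-pregnancy period ends, and apply to subjects and partners of male subjects.
- At the existing last visit, instruct subjects to report any pregnancy within that period, and check that the consent text says the same.

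The cost is an amendment, matching consent wording, one instruction at a visit already planned, and following any pregnancy reported after the study to its outcome. No visit or test is added.

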4.2 Exclusion Criteria

Cohorts 1-3:

Subjects must be excluded if any of the following criteria are met:

1. Participation in other IP or device clinical trials within 30 days prior to Day 0, or planning to participate in other IP or device clinical trials within 60 days following the first study day. This includes both ocular and non-ocular clinical trials.
2. Female subjects who are pregnant, nursing, or planning a pregnancy, or who are of childbearing potential and not willing to use reliable means of contraception.
3. Subjects with a known allergy or hypersensitivity to the study medication, any component of the delivery vehicle, any corticosteroids or any diagnostic agents used during the study (e.g., fluorescein, dilation drops, antibiotic drops, povidone).
4. Subjects who have regularly used any ocular agents within 60 days prior to Day 0.

Cohort 4:

Subjects must be excluded if any of the following criteria are met:

5. Participation in other IP or device clinical trials within 30 days prior to Day 0, or planning to participate in other IP or device clinical trials within 60 days following the first study day. This includes both ocular and non-ocular clinical trials.
6. Female subjects who are pregnant, nursing, or planning a pregnancy, or who are of childbearing potential and not willing to use reliable means of contraception.
7. Subjects with a known allergy or hypersensitivity to the study medication, any component of the delivery vehicle, any corticosteroids or any diagnostic agents used during the study (e.g., fluorescein, dilation drops, antibiotic drops, povidone).
8. Subjects who have regularly used any ocular agents within 60 days prior to Day 0 except topical lubricants.

5. STUDY DRUG ADMINISTRATION

See Section 8 for a complete description of study drugs. The study drug will be supplied ready to use.

This is a randomised, placebo-controlled study and double blinded within each cohort

Each subject who completes the study screening assessments, meets all eligibility criteria, and is accepted for the study will be assigned a unique identification number and will receive the corresponding study medication (PP-001 or placebo) according to a randomization schedule

Medication will be provided in pre-labelled, blinded, treatment bottles.

The site will be provided with code-break envelopes by which they can break the blind if required. The Investigator should contact the Sponsor prior to breaking the blind unless the subject's safety may be put at risk by doing so.

5.1 Study Drug Treatment

5.1.1 Duration of Treatment

Subjects will receive up to four eye drops of PP-001 per day in a randomly assigned eye. Subjects will be treated initially for 1 day (Day 0) and then for 12 days (4 times daily, Days 8–19) in cohorts 1-3 and for 12 consecutive days (2 times daily, Days 0-11) in cohort 4.

5.1.2 Post-Baseline Treatment Modifications

Cohorts 1 to 3 will be performed in dose ascending order. On the first two study days in Part I of each cohort, one subject will be dosed per day. On the third study day up to two subjects can be dosed per day. On the following study day(s) up to 4 subjects can be dosed per day. Randomization will be performed in two blocks (3:1, PP-001 vs. placebo) for each cohort. Part II will start at least 7 days after the last subject has been dosed in Part I and the Principal Investigator and the sponsor decide whether or not to continue dosing the cohort in Part II. The DSMB will decide if the safety and tolerability demonstrated in Parts I and II of the previous cohort warrant continuing the study at the next highest dose.

Subjects in cohort 4 will instill the eye drops only twice daily.

5.2 Timing of Dosing and Dose Administration

Cohorts 1-3:

Subjects will receive IP on Day 0 (single dose) and then Days 8–19 (48 doses).

On Day 0, the IP dose will be administered in house by site staff. Staff will administer a single drop of IP into one eye.

On Day 8 and 9, the IP doses will be administered in house by site staff. Staff will administer a single drop of IP into one eye four times throughout the dosing day separated by at least 4 hours.

On Days 10–19, the IP will be self-administered. Subjects will administer a single drop of IP into one eye four times throughout each dosing day separated by at least 4 hours.

Cohort 4:

Subjects will receive IP on Days 0-11 (24 doses).

On Day 0 and 1, the first instillation will be performed in house by site staff. Staff will administer a single drop of IP into one eye. At all following time points, the IP will be self-administered. Subjects will administer a single drop of IP into one eye two times throughout each dosing day separated by at least 8 hours.

Since only one randomly assigned eye will be treated, subjects will be handed out a bottle of topical lubricants (Genteal HA, Laboratoires Thea, France) as standard of care treatment for the control eye as needed. Subjects will be instructed to document instillation dates and times for Genteal HA eye drops in the diary.

5.3 Preparation of Treatment

A Pharmacy Manual will be provided to investigative sites with additional details on preparation of study drug material.

5.4 Blinding

This is a double-blind study within each cohort. Subjects will receive either PP-001 or placebo. Randomization will be done in two blocks of 4 subjects per block (3:1, PP-001 vs. placebo) for each of the three cohorts (cohorts 1-3). For cohort 4, randomization will be performed in a 2:1 ratio (14 subjects will receive the PP-001 and 7 will receive placebo). Subjects within one cohort will not be aware whether they are receiving PP-001 or placebo. The investigators will not know whether a subject receives PP-001 or placebo within a cohort. The IP will be provided in pre-packaged eye drop bottles which will be labelled in a double-blind fashion.

